7.6.1.3 Reporting Periods for Adverse Events and Serious Adverse Events

The safety reporting period for all AEs and SAEs is from study Day 1 (during and post-dosing) up to 30 days after the last study treatment dose. For those undergoing retreatment, the safety reporting period will also include retreatment study Day 1 (during and post-dosing) up to 30 days after the last study retreatment dose. However, all study protocol-procedure related AEs and SAEs are to be recorded from the time of informed consent. Additionally, all SAEs that occur after the safety reporting period that are considered study treatment-related in the opinion of the investigator should also be reported to the sponsor or its designee.

Each SAE must be followed until the SAE is Recovered/Resolved, Not recovered/Not resolved, Recovered/Resolved with sequelae, or the subject dies (the SAE may be assessed as ongoing at the time of death). SAE outcomes may not be possible to collect when a subject withdraws consent and/or is lost to follow-up. All non-serious AEs will be followed through the end of the safety reporting period. Certain non-serious AEs of interest should be followed until resolution, return to baseline, or study closure.

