5.4 Concomitant Therapy

All concomitant medications, blood products, procedures and radiotherapy administered will be recorded from Day 1 (predose) through the safety reporting period. Any concomitant therapy given for a study protocol-related adverse event should be recorded from the time of informed consent.

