6 STUDY ACTIVITIES

6.1 Enrollment

Once screening procedures have been completed for the subject, the Registration and Enrollment Form will be completed and submitted to the sponsor or designee to confirm eligibility. Refer to the Study Manual for enrollment form, contact numbers, and other details of enrollment.

AEs and concomitant therapies will be recorded from Day 1 (predose) through the safety reporting period. At the same time, subjects will maintain a diary of daily weights. Any study protocol-related adverse event should be recorded from the time of informed consent as well as any concomitant therapies given for treatment of the adverse event. A schedule of events is provided in Appendix 12.1. Study activities are listed by visit in this section and descriptions of all study assessments are presented in Section 7.

Subjects undergoing retreatment as described in Section 3.1 will follow the same study schedule from Screening through EOT and LTFU.

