6.3 Treatment Period

The treatment period for subjects is Day 1 to 42 of each 6 week cycle. Subjects undergoing retreatment as described in Section 3.1 will follow the same study schedule from Screening through EOT and LTFU.

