6.4 End of Treatment Visit

The EOT visit occurs 42 ± 3 days after last dose of study drug or within 7 days of documentation of the decision to discontinue treatment, whichever is later.

- Physical examination (see Section 7.6.2)
- Vital signs (see Section 7.6.3)
- Complete blood count (see Section 7.6.4)
- Chemistry Panel (see Section 7.6.4)
- Coagulation tests (see Section 7.6.4)
- Urinalysis (see Section 7.6.4)
- Pregnancy test (see Section 7.6.4) for women of child-bearing potential
- Triplicate ECG (see Section 7.6.5)
- Echocardiogram (see Section 7.6.6)
- ECOG performance status (Appendix 12.2)
- Fluid retention questionnaire (see Section 7.6.8)
- Disease assessment consisting of CT scans of the chest, abdomen, and pelvis (and neck if indicated) – may be omitted if a Disease/Response Assessment was performed within the last 6 weeks (see Section 7.2)
- MRI of the brain – if clinically indicated (e.g. if CNS progression has been documented previously); may be omitted if a Disease/Response Assessment was performed within the last 6 weeks. For those subjects that are unable to tolerate MRI, a CT scan with contrast can be performed instead (with approval from the Medical Monitor)

- Blood sample for pharmacokinetics
- Blood sample for anti-therapeutic antibodies
- Blood inflammatory markers (see Section 7.4.2)
- Blood tumor markers (see Section 7.4.3)
- Soluble biomarkers (see Section 7.4.4)
- [REDACTED]

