7.6.1 Adverse Events

7.6.1.1 Definitions

Adverse Event

Per the International Conference on Harmonization (ICH) E2A Guidance, Clinical Safety Data Management: Definitions and Standards for Expedited Reporting ([ICH, 1995](#)), and 21 CFR 312.32 IND Safety Reporting, an AE is any untoward medical occurrence in a patient or clinical

investigation subject administered a pharmaceutical product and which does not necessarily have a causal relationship with this treatment.

The following information should be considered when determining whether or not to record a test result, medical condition, or other incident on the Adverse Events or Pre-existing Conditions case report form (CRF):

- From the time of informed consent through Day 1 prior to dosing, only study protocol-related AEs and serious adverse events (SAEs) should be recorded. A protocol-related AE is defined as an untoward medical event occurring as a result of a protocol mandated procedure.
- All baseline medical conditions present prior to dosing on study Day 1 should be recorded and assessed for grade or severity.
- All AEs (regardless of relationship to study drug) should be recorded from study Day 1 (during and post-dose) through the end of the safety reporting period (see Section 7.6.1.3). Complications that occur in association with any procedure (e.g., biopsy) should be recorded as AEs with assessed grade or severity whether or not the procedure was protocol mandated.
- Changes in baseline medical conditions and AEs (including changes in severity, frequency, or character) during the safety reporting period should be recorded.
- In general, an abnormal diagnostic or laboratory value should not be recorded as an AE unless it is associated with clinical signs or symptoms (i.e. assessed as clinically significant), requires an intervention, results in a serious adverse event (SAE), or results in study termination or interruption/discontinuation of study treatment. When recording an AE resulting from a diagnostic or laboratory abnormality, the medical condition or diagnosis rather than the abnormality itself should be recorded (e.g., record “anemia” rather than “low hemoglobin”).

Serious Adverse Event (SAE)

A serious adverse event (SAE) is any untoward medical occurrence that at any dose:

Fatal: Results in death.

Life threatening: Is life threatening.

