7.6.1.2 Procedures for Eliciting and Recording Adverse Events

Investigator and study personnel will report all AEs and SAEs whether elicited during subject questioning, or discovered during physical examination, laboratory testing and/or other means by recording them on the CRF and/or SAE form, as appropriate.

Eliciting Adverse Events

An open-ended or non-directed method of questioning should be used at each study visit to elicit the reporting of AEs.

Recording Adverse Events

The following information should be recorded on the Adverse Events and Pre-existing Conditions CRF:

- Description using standard medical terminology (with an effort to use the unifying or reached diagnosis), including onset and resolution dates
- Whether the AE met serious criteria
- Severity/Grade
- Relationship to study treatment or other causality
- Outcome

Diagnosis vs. Signs or Symptoms

In general, the use of a unifying or reached diagnosis is preferred to reporting of individual symptoms. Grouping of symptoms into a diagnosis should only be done if each component sign and/or symptom is a medically confirmed component of a diagnosis as evidenced by standard medical practice. If any aspect of a sign or symptom does not fit into a classic pattern of the diagnosis, report the individual symptom as a separate adverse event.

Important exceptions for this study are adverse reactions associated with the infusion of study drug. For infusion-related reactions, do not use the NCI CTCAE terms of ‘cytokine release syndrome,’ ‘acute infusion reaction,’ or ‘allergic or hypersensitivity reaction.’ Instead, record each sign or symptom as an individual AE. If multiple signs or symptoms occur with a given infusion-related event, each sign or symptom should be recorded separately with its own level of severity.

Recording Serious Adverse Events

For SAEs, record the event(s) on both the CRF and an SAE form.

The following should be considered when recording SAEs:

Death is an outcome of an event. Death, per se, is not a reportable event. The event that resulted in the death should be recorded and reported on both an SAE form and CRF.

For hospitalizations, surgical, or diagnostic procedures, the illness leading to the surgical or diagnostic procedure should be recorded as the SAE, not the procedure itself. The procedure should be captured in the narrative as part of the action taken in response to the illness.

Progression of the Underlying Cancer

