12 APPENDICES

12.1 Schedule of Assessments

Item	Location	Screening		Every Treatment Cycle						EOT ¹	LTFU				
		Day	Window	-14 to -1	-1	1 ²	2	3	8	15	22	29	36	42 days after last dose	q6-12 w thru 4 yr ⁴
	Clinic Visit	X	-			± 2d ²	-	± 1d	± 2d	± 2d	± 3d	± 3d	± 3d	± 3d	± 1w
	Virtual Visit							X		X		X		X	
	Investigator (MD) present	X						X		X		X		X	
Screening, Baseline, and Safety Assessments	Informed Consent ⁵	X						X		X		X		X	
	Demographics	X													
	Inclusion/Exclusion Criteria	X													
	Medical and Surgical History ⁶	X													
	Malignancy History ⁷	X													
	Prior Anticancer Treatments ⁸	X													
	Physical examination	X								X		X		X	
	Vital Signs ⁹	X						X		X		X		X	
	Height	X													
	Complete Blood Count ¹⁰	X								X		X		X	
	Chemistries ¹¹	X								X		X		X	
	Coagulation Tests ¹²	X								X		X		X	
	Urinalysis ¹³	X								X		X		X	
	Hepatitis B and C tests ¹⁴	X													
	Pregnancy Test ¹⁵	X												X	
	Electrocardiogram (ECG) ¹⁶	X							X					X	
	Echocardiogram ¹⁷	X												X	
	Performance Status (ECOG)	X												X	
	Fluid Retention Questionnaire ¹⁸	X								X		X		X	
	Daily Weight Diary ¹⁹														
Treatment	Concomitant Therapies ²⁰ only														
	Rovalpituzumab tesirine							X		X					
	Dexamethasone							X		X					
Response Assessment	Disease/Response Assessment ²¹ , ₂₃	X										X		X ²²	X
	MRI of the Brain	X										X ²⁴		X ²⁴	
	Paraneoplastic Assessment ²⁵	X													

Day 1 predose thru EOT or 30 days after last study treatment, whichever is later

Schedule of Assessments Cont.

Item		Every Treatment Cycle										EOT ¹ 42 days after last dose	LTFU q6-12 w thru 4 yr ⁴ ± 1w
		Screening	Day -14 to -1	-1	1 ²	2	3	8	15	22	29	36	
Day	Window	Day	Window	Day	Window	Day	Window	Day	Window	Day	Window	Day	Window
PK, PD and Biomarkers	Pharmacokinetics ²⁶	-	-	± 2d ²	-	± 1d	± 2d	X	± 2d	± 2d	± 3d	± 3d	± 3d
	Anti-therapeutic antibody			X									X
	Tumor Tissue ²⁷	X											X
	Inflammatory Markers ²⁸			X									X
	Blood Tumor Markers ²⁹			X									X
	Soluble Biomarkers ³⁰			X									X
				X									X
													Day 1 thru EOT or 30 days after last study treatment, whichever is later

Table Notes

- 1) EOT occurs 42 ± 3 days after last dose, or within 7 days of documentation of the decision to discontinue treatment, whichever is later.

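### AE reporting ends 30 days after the last dose, 9 to 15 days before the scheduled End of Treatment safety visit and earlier than the Schedule of Assessments indicates, so late AEs may be recorded unevenly

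*Protocol*

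**What the plan says.** **The reporting period.** Protocol Section 7.6.1.3 says that the window for safety reporting "for all AEs and SAEs is from study Day 1 (during and post-dosing) up to 30 days after the last study treatment dose". It sets the same 30-day end after the last retreatment dose. Non-serious AEs are followed only to the end of that period, apart from certain AEs of interest. After it, SAEs that the investigator considers treatment-related must still be reported.

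**Sections that take their end from it.**
- Section 6.1: "AEs and concomitant therapies will be recorded from Day 1 (predose) through the safety reporting period".
- Section 7.6.1.1: AEs of any relationship "should be recorded from study Day 1 (during and post-dose) through the end of the safety reporting period".
- Section 5.4: concomitant medications and other therapies "administered will be recorded from Day 1 (predose) through the safety reporting period".

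**The EOT visit.** Section 6.4: "The EOT visit occurs 42 ± 3 days after last dose of study drug", or within 7 days of the documented decision to stop treatment if that is later. The visit includes physical examination, laboratory tests, triplicate ECG, echocardiogram and the fluid retention questionnaire.

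**The Schedule.** Appendix 12.1 carries the span "Day 1 predose thru EOT or 30 days after last study treatment, whichever is later".

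**The SAP.** Section 6 counts an AE in the initial course as treatment-emergent from first dose until retreatment or a subsequent anti-cancer therapy, with no limit in days. Sections 7.7.2 and 7.7.4 accept EOT laboratory and ECG results up to 45 days after treatment discontinuation. Section 7.7.5 tabulates pericardial effusion at each scheduled visit. Section 7.7.7 limits concomitant medications to 30 days after the last dose.

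**The concern.** The protocol appears to give two different ends for AE recording, and the earlier one closes before the last safety visit of each course. A site that follows Section 7.6.1.3 may leave an event with onset on day 35 unrecorded. A site that follows the Schedule would record it. Both act within the protocol.

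Pericardial effusion is the clearest example. Section 1.1.3 lists serosal effusions among the remarkable toxicities. By the visit lists (Sections 6.3.2 and 6.4), echocardiograms fall on Day 1 of a cycle and at EOT, so the only one scheduled after the last dose of a course comes after the reporting period has closed. Appendix 12.5 describes a Grade 2 pericardial effusion as asymptomatic, so it may first be seen on that scan. It would enter the SAP shift table. If its onset is dated to the scan and it is not serious, Section 7.6.1.3 requires no AE record.

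Safety and tolerability are a secondary objective. TEAE tables that combine required recording up to day 30 with incidental recording afterwards would give late-event rates that depend partly on which section each site followed.

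**Working it through.** The plan states no figure for this gap, so there is none to reproduce. The check is day arithmetic.

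**Inputs**
- End of reporting period: day 30 after the last dose (Protocol 7.6.1.3).
- EOT: day 42 ± 3 after the last dose (Protocol 6.4), so 42 − 3 = 39 to 42 + 3 = 45.
- Schedule span: the later of EOT and day 30 (Appendix 12.1).
- Planned course: two doses 42 days apart (Protocol 3.2.2), assuming no delay.

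**Step 1. Where the Schedule span ends.** It is max(EOT day, 30). For every EOT day from 39 to 45 this equals the EOT day, so the span always outlasts Section 7.6.1.3, by at least 9 days.

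**Step 2. Gap and its share of time.** Gap = EOT day − 30. Course length = 42 + EOT day.

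| EOT day | Gap (days) | Share of last dose to EOT | Share of two-dose course |
|---|---|---|---|
| 39 | 39 − 30 = 9 | 9/39 = 23% | 9/81 = 11% |
| 42 | 42 − 30 = 12 | 12/42 = 29% | 12/84 = 14% |
| 45 | 45 − 30 = 15 | 15/45 = 33% | 15/87 = 17% |

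**Step 3. A late decision to stop.** If the decision is documented on day D after the last dose, EOT may fall as late as D + 7. The documents give no distribution for D, so these values are assumptions:
- D = 42: EOT up to day 49, gap up to 19 days.
- D = 60: EOT up to day 67, gap up to 37 days.
- D = 84 (a 42-day cycle plus the 6-week maximum interruption in Table 5-3): EOT up to day 91, gap up to 61 days.

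Fifteen days is therefore the limit for the 42 ± 3 day visit, not an overall maximum.

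**Step 4. Other contacts in the gap.** With Day 1 as the dosing day, the Day 36 ± 3 fluid retention contact falls 32 to 38 days after the dose, also beyond day 30. SAP Section 4.5 says that questionnaire data are not entered or analysed, so the questionnaire itself supplies no analysed record of a problem raised there.

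**Step 5. What is and is not required after day 30, reading Section 7.6.1.3 as written**
- Required: treatment-related SAEs; follow-up of certain non-serious AEs of interest. Section 5.5.2 also asks for cutaneous toxicity to be monitored to resolution or return to baseline.
- Not required: new non-serious AEs, and new SAEs judged unrelated.
- Analysed in any case: EOT laboratory, ECG and echocardiogram results.

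**Step 6. Which Schedule row carries the span.** The table layout is broken in the available text, so the row has to be inferred. The span starts predose on Day 1, which is the start that Section 6.1 gives for AEs and concomitant therapies together. The SAP's copy of the Schedule has an AE row marked as procedure-related only, and a stray fragment of that entry seems to stand beside concomitant therapies in the protocol's copy. If the span covers concomitant therapies alone, it still conflicts with Sections 5.4 and 6.1, which end their recording with the same safety reporting period.

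**The case against.** The best defence is that the text is consistent and only a damaged table disagrees. Sections 5.4, 6.1 and 7.6.1.1 all defer to Section 7.6.1.3, and SAP Section 7.7.7 uses 30 days as well. A nearly identical span also appears in the biomarker part of the Schedule, so the wording is not specific to AEs. It stands that the AE row is inferred and should be checked in the formatted protocol. The defence does not remove the conflict, for the reason in Step 6.

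A reader might go further and infer any of the following. The documents do not support them.

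- *That AE questioning contradicts the reporting period.* Section 7.6.1.2 says: "An open-ended or non-directed method of questioning should be used at each study visit to elicit the reporting of AEs". Questioning at EOT also finds events that began by day 30, after the Day 29 visit. How AEs are elicited is a separate matter from which onset dates are reportable.
- *That other sections set a second end date.* Section 6.3 ("The treatment period for subjects is Day 1 to 42 of each 6 week cycle") defines a cycle. Section 4.3 asks for safety data that are normally required anyway. Section 7.6.1.6 says when a laboratory result counts as an AE and needs no end date of its own.
- *That EOT safety data or serious drug toxicity are lost.* EOT measurements are analysed, and treatment-related SAEs remain reportable without limit.
- *That about 29% of AEs are missed.* That figure is a share of time in the final interval only.

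It also stands that the affected group is narrow and that a single-arm trial has no between-arm comparison to bias. Section 3.2.2 mentions delayed and/or cumulative toxicities but gives no onset times, so it cannot size the problem.

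**Conclusion.** The concern holds as a mismatch between the reporting period, the EOT visit and the Schedule. Recording closes nominally 12 days (9 to 15) before the scheduled EOT visit, and earlier still relative to EOT when a late decision to stop sets that visit. The gap is 23 to 33% of the interval from last dose to EOT. Over an undelayed two-dose course it is 11 to 17%; the larger share describes a whole course only for subjects who receive one dose.

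The consequence is uneven capture across sites of non-serious AEs, and of SAEs judged unrelated, with onset between day 30 and EOT. The open-ended TEAE window does not cause this, but it lets the unevenness into the tables. The number of AEs affected cannot be derived from the documents.

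The conclusion assumes that the Schedule span applies to AEs, or at least to concomitant therapies, and that some sites would follow Section 7.6.1.3 literally. It is worth correcting for the safety objective and does not bear on the primary efficacy endpoints.

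**What to change.** - **Protocol 7.6.1.3:** define the safety reporting period as ending at the later of the EOT visit and day 30 after the last dose, separately for initial treatment and for retreatment. This is the Schedule's own rule. Sections 5.4, 6.1 and 7.6.1.1 then follow by reference.
- **Appendix 12.1:** confirm that the span is on the AE and concomitant-therapy rows.
- **SAP 7.7.7:** replace the 30-day limit for concomitant medications with the same period, and reconcile it with the open-ended definition in SAP Section 6.
- **SAP Section 6, TEAE definition:** leave it open-ended. Cutting it at EOT would move later treatment-related SAEs out of the TEAE tables. Add a table footnote that, after EOT, only treatment-related SAEs are required to be reported.

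Shortening the Schedule to day 30 would also make the texts agree, but new findings at EOT would still need no AE record.

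**Cost.** About 12 more days (9 to 15) of AE recording per course, collected at a visit already scheduled, and longer where EOT is late. It also needs a protocol amendment with ethics committee approval, one SAP edit and one footnote.

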7.6.1.4 Serious Adverse Events Require Immediate Reporting

Within 24 hours of observing or learning of a SAE, investigators are required to report the event to the sponsor or designee, regardless of the relationship of the event to the study treatment regimen.

For initial SAE reports, available case details are to be recorded on a SAE form. At a minimum, the following must be included:

- Identifiable subject with identification number (can also include gender, age at onset)
- Study treatment (suspect medicinal product)
- Identifiable reporting source
- An event or outcome that can be identified as serious, preferably with a description of the event with date of event onset (to reflect latency)
- Causality (relatedness)

The completed SAE form are to be transmitted to the Drug Safety Department of the sponsor or designee (see contact information specified on the SAE report form) within 24 hours.

Relevant follow-up information is to be submitted to the sponsor as soon as it becomes available.

7.6.1.5 Sponsor Safety Reporting to Regulatory Authorities

Investigators are required to report all SAEs, including anticipated SAEs, to the sponsor or designee (see Section 7.6.1.4).

The sponsor or designee will report all SAEs to the appropriate regulatory authorities as required per local regulatory reporting requirements. In the United States, endpoints that assess disease-related mortality or major morbidity as well as other SAEs that are not study endpoints (but are known consequences of the underlying disease or condition that are anticipated to occur in the

study population), should not be reported to the FDA as individual IND safety reports (per the final rule amending the IND safety reporting requirements under 21 CFR 312.32 and the FDA's guidance Safety Reporting Requirements for INDs and BA/BE Studies dated December 2012).

7.6.1.6 Laboratory Test Result Abnormalities

Any laboratory test result abnormality should be reported as an AE or SAE, as appropriate, if it:

- is clinically significant or meets the definition of an SAE
- required the subject to have study drug discontinued or interrupted
- required the subject to receive specific corrective therapy

Wherever possible, the medical diagnosis rather than laboratory term should be used by the reporting Investigator (e.g., use "anemia" rather than "low hemoglobin").

7.6.1.7 Potential Drug-Induced Liver Injury

Wherever possible, timely confirmation of initial liver-related laboratory abnormalities should occur prior to reporting a potential drug-induced liver injury (DILI) event ([FDA 2009](#)). All occurrences of potential DILIs, meeting the defined criteria, must be reported as SAEs.

Potential drug-induced liver injury is defined as:

- ALT or AST elevation > 3 times (3X) upper limit of normal (ULN); AND
- Total bilirubin > 2X ULN, without initial findings of cholestasis (elevated serum alkaline phosphatase), AND
- No other immediately apparent possible causes of aminotransferase (AT) elevation and hyperbilirubinemia, including, but not limited to, viral hepatitis, pre-existing chronic or acute liver disease or tumor(s), or the administration of other drug(s) known to be hepatotoxic

In general, an increase of serum AT to > 3X ULN should be followed by repeat testing within 48-72 hours of all four of the usual serum measures (ALT, AST, alkaline phosphatase, and total bilirubin) to confirm the abnormalities and to determine if they are increasing or decreasing.

Inquiry regarding symptoms should also be made (e.g., fatigue, nausea, vomiting, right upper quadrant pain or tenderness, fever, rash). Subjects may be retested locally, but normal laboratory ranges should be recorded and results made available to the investigator immediately for review. All data must be recorded on the case report forms. Close observation should be initiated if symptoms persist or repeat testing shows AT >3xULN for subjects with normal baseline

measures or 2-fold increases above baseline values for subjects with elevated values before drug exposure. If close monitoring is not possible, study drug should be discontinued.

Close observation includes:

- Repeating liver enzyme and serum bilirubin tests two or three times weekly. Frequency of retesting can decrease to once a week or less if abnormalities stabilize or the study drug has been discontinued and the subject is asymptomatic.
- Obtaining a more detailed history of symptoms and prior or concurrent diseases.
- Obtaining a history of concomitant drug use (including non-prescription medications and herbal and dietary supplement preparations), alcohol use, recreational drug use, and special diets.
- Ruling out acute viral hepatitis types A, B, C, D, and E; autoimmune or alcoholic hepatitis; NASH; hypoxic/ischemic hepatopathy; and biliary tract disease.
- Obtaining a history of exposure to environmental chemical agents.
- Obtaining additional tests to evaluate liver function, as appropriate (e.g., INR, direct bilirubin).
- Considering gastroenterology or hepatology consultations.

Discontinuation of study drug should be considered if potential DILI is suspected and:

- ALT or AST $> 8x$ ULN
- ALT or AST $> 5x$ ULN for more than 2 weeks
- ALT or AST $> 3x$ ULN and (TBL $> 3x$ ULN or INR > 1.5)
- ALT or AST $> 3x$ ULN with the appearance of fatigue, nausea, vomiting, right upper quadrant pain or tenderness, fever, rash, and/or eosinophilia

All trial subjects showing possible DILI should be followed until all abnormalities return to normal or to the baseline state. Retreatment of subjects who develop possible DILI and have previously discontinued study drug may only be permitted upon approval by the sponsor and medical monitor.

